4.3 Demographics and Baseline Characteristics

Descriptive statistics or frequency tabulation will be provided for the following parameters. The 'Declined to answer/don't know' will not be added for the denominator unless stated otherwise.

4.3.1 Demographic Parameters

Descriptive statistics or frequency tabulation will be provided for following parameters (Table 14.1.4.1):

- Age (years) : calculated as the integer part of (Date of Informed Consent – Date of Birth + 1)/365.25
- Sex (Male, Female)
- Race (Caucasian, Black or African American, Asian, American Indian or Alaskan Native, Native Hawaiian or Other Pacific Islander, Other Race, Multiple – derived if multiple races are checked, Not Done/Refused)
- Ethnicity (Hispanic or Latino, Not Hispanic or Latino)
- Education Level (No high school, Some High School, High school diploma/GED, Undergraduate, Masters, Doctoral, Unknown)
- Marital status (Single, Married, Widowed, Divorced/Separated)
- Family size
- Longest held career (Professional, Homemaker, Trade person, Arts/Entertainment, Declined to answer/Don't know, Other)
- Highest historical level of annual household income ever reported (Less than \$50,000, \$50,000 to \$99,999, \$100,000 to \$199,999, \$200,000 or more, Declined to answer/Don't know).
- Weight at baseline (kg)
- Height at baseline (cm)
- Body Mass Index (BMI) at baseline = Weight at baseline (kg) / [Height at baseline (m)]² (rounded to 1 decimal. Although available in the raw data, BMI will be recalculated from last weight and height measurement before start of treatment)
- Duration of AD (years)
- Any Prior Treatments for AD (Yes/No)

4.3.2 Baseline Assessment of Modified Hachinski Ischemia Scale (MHIS)

No tabulation summary will be provided for MHIS data, which will be included in a subject data listing only.

4.3.3 APOE Genotype

Frequency tabulation will be provided for APOE Genotype (E2/E2, E2/E3, E2/E4, E3/E3, E3/E4, E4/E4) (Table 14.1.4.2)

4.3.4 Echocardiogram Baseline Assessment

No tabulation summary will be provided for echocardiogram data, which will be included in a subject data listing only.

4.4 Medical History

The investigator or designee will obtain a detailed medical history through interview with the subject and the subject's caregiver(s) during screening. The medical history should focus on recent history, with an emphasis on the history of cognitive symptoms related to probable AD. Additionally, the medical history should include:

- Current/past illnesses and conditions

- Current symptoms and any active medical condition
- Surgeries and procedures
- Allergies
- Family history in biological parents, siblings, and offspring of AD, other dementias, or neurological disorders, if known.
- Social history (e.g. smoking, alcohol, illegal substances), if known.
- Prior imaging, cerebrospinal fluid assessments, or other relevant diagnostic tests, including genetics, if available.

4.4.1 Subject Medical History

All reported subject medical history findings will be summarized by MedDRA system organ class and preferred term, in order of descending overall frequency (Table 14.1.5.1).

4.4.2 Family Medical History

All reported family medical histories will be listed by type of family member (Father, Mother, Brother, Sister, Son, Daughter, Half-Brother, Half-Sister) for following parameters:

- Status (Living, Deceased)
- Cause of death
- Age at time of death (Years)
- History of neurological disease (Any, Alzheimer's, Parkinson's, Lewy body dementia, Frontotemporal dementia, Amyotrophic Lateral Sclerosis (ALS) or Lou Gehrig's disease, Vascular dementia, Other neurological Family Hx)

4.4.3 Social History

A frequency tabulation will be summarized for the following parameters (Table 14.1.5.2):

- Current Living Situation (In my home, In a relative or friend's home, In a care facility, Other, Declined to answer/don't know)
- Living conditions (Alone, With Family, With a Friend(s)/Roommate(s), With a Professional Caregiver, With One or More Pets, Declined to answer/don't know). Various living conditions will be arranged in order of descending overall frequency.

4.4.4 Tobacco Use

Descriptive statistics or frequency tabulation will be provided for the following parameters related to tobacco use (Table 14.1.5.3):

- Smoking status (Never Smoked, Current Smoker, Ex-Smoker)
- Number of years smoked
- Average cigarettes/day
- Average pipes/day
- Average cigars/day
- Average cigarettes, pipes or cigars/day (derived by adding average cigarettes/day, average cigars/day, and average pipes/day)

4.4.5 Alcohol and Illicit Substance Use

Frequency tabulation will be provided for the following parameters related to alcohol and illicit substance use (Table 14.1.5.4):

- Consumed alcohol in past 6 months (Yes, No)
- Problem with alcohol when young (Yes, No, Declined to answer)
- Used illicit substances in the past (Yes, No)

4.5 Prior and Concomitant Medications

Subject's current medications, including over-the-counter drugs, herbal supplements and/or vitamins, as well as those taken by the subject in the past 12 months (including previous treatments for AD) will be coded using the World Health Organization-Drug Dictionary and summarized separated for each of following two categories:

- 1) Prior medication: medication that ended before the first dose of study drug.
- 2) Concomitant medication: medication received at or after the first dose of study drug, medication that was received before initial dosing and continued after initial dosing of study drug, or medication with missing stop date.

A frequency tabulation of prior and concomitant medications will be shown by ATC class level 4 and preferred term (Table 14.1.6.1 and 14.1.6.2).

4.6 Extent of Exposure

The extent of exposure (days) is defined as date of last study drug intake – date of first study drug intake + 1 within the dosing period. For subjects that have a “grace day” (i.e. they received 5 infusions over a period of 6 days instead of 5 infusions over 5 consecutive days), such dosing “grace day” is not considered an interruption. Extent of exposure as well as actual volume administered will be summarized descriptively overall (Table 14.1.7.1).

Descriptive statistics of actual infusion rate (mL/hour) will be summarized at each time point per infusion day (Table 14.1.7.2). The numbers of below, within and above the designated infusion rate reference will be tabulated at each time point per infusion day (Table 14.1.7.3). In addition, descriptive statistics or frequency tabulation will be provided for the following infusion parameters collected at each infusion day (Table 14.1.7.4):

- Required adjustment to flow rate (Yes, No)
- Entire assigned dose administered (Yes, No)
- Actual Volume Administered (mL)
- Maximum flow rate (mL/hour)
- Volume of Saline Flush
- Device used to administer infusion (Baxter Flo Gard, Other)

Unscheduled changes in flow rate will be included in the subject data listing only

4.7 Treatment Completion

Treatment completion is calculated as the actual volume administered, as a percentage of the volume expected. The expected dose overall will be calculated

as [5 x total daily dose volume] for all subjects, regardless of study completion status. Treatment completion will be summarized descriptively and categorically (<75% and >=75%) overall (Table 14.1.8.1).

In addition, number of subjects completing 1, 2, 3, 4, and 5 infusions will be summarized (Table 14.1.8.2).

4.8 Tolerability

Number of subjects completing 4 weeks after receiving at least 5 infusions will be tabulated (Table 14.1.9).

4.9 Visit Compliance

Number of subjects with a visit at each scheduled analysis timepoint will be summarized (Table 14.1.10).

5 EFFICACY

The study is not powered to detect significant changes in cognition, function, ADLs, etc.; however, using available data from analysis of the secondary efficacy endpoints, including changes in scores from baseline, descriptive summaries will be developed. Of particular interest will be the within-subject changes from baseline and their distribution around a null value of zero and a comparison between groups to evaluate any trends in differences between subjects randomized to active and placebo agents.

For analysis purposes, results at early termination visits will not be included in tabulated summaries unless the number of early termination visits is > 5.

Following efficacy endpoints will be analyzed based on both EVAL and PPROT sets.

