10.4 DESCRIPTION OF STATISTICAL METHODS

10.4.1 GENERAL APPROACH

Using the Evaluable and/or Per Protocol Datasets, all secondary endpoints will be summarized serially over time using descriptive statistics to assess the within-subject changes and between-group differences. Overall baseline and demographic data will be summarized using descriptive statistics; between-groups testing will be used to evaluate the effectiveness of the randomization in producing homogeneous pre-treatment groups.

Subject disposition (e.g., the number of subjects randomized, completed, and discontinued) will be summarized, and medical history data will be listed. Prior and concomitant medications taken from Screening and during the study will be categorized by World Health Organization classification for therapeutic class and drug name, listed and summarized by number and percentage of subjects.

Final analyses are not limited to the summaries described herein. As noted above, analytical details and assumptions will be fully presented in the SAP.

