1.4 Randomization and Blinding

To minimize the potential bias at the time of randomization, the study will be double-blind and randomized with a 2:1 ratio to GRF6019 (Group 1) or placebo (Group 2). A stratified block randomization will be implemented by sex. The randomization codes will be generated by a statistician who has no involvement in the study other than generation and maintenance of the randomization codes.

All study outcome measures will be assessed by blinded Outcomes Assessors or other blinded raters. However, [REDACTED] GRF6019 or placebo will be dispensed by an unblinded pharmacist, or other qualified staff responsible for drug accountability, to an unblinded Infusion Nurse who will administer the infusion. To ensure that Outcomes Assessors, raters, and other study personnel as well as subjects and their caregivers are unaware of the allocation, appropriate measures will be taken to mask the study agent/placebo containers and IV setup such that they will only be visible as necessary to the unblinded Infusion Nurse. In addition, a curtain, drape, or equivalent may be used to shield the infusion administration setup from view of all but the unblinded Infusion Nurse, and the unblinded Infusion Nurse will be responsible for concealing and returning used containers of the study agent or placebo to the pharmacy at the end of the Infusion Period. The unblinded Infusion Nurse will

enter the infusion data and blinding assessment into the eCRF to avoid unblinding of the source data during data entry.

During the infusion, communication between the blinded Outcomes Assessor and the unblinded Infusion Nurse should be limited to only that required to ensure the immediate safety of subjects. The Outcomes Assessors will observe the subject during the infusion and collect and/or manage/report AEs and SAEs.

Except for the unblinded CRA(s) whose sole responsibility is to ensure the study agent/placebo is being dispensed, administered, and disposed of properly, the study Sponsor and their representatives will be blinded with respect to the infusion product.

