2.2 Statistical Hypothesis Tests

Because the primary objective of the study is safety and tolerability, it is not designed to detect statistically significant differences between active and placebo efficacy endpoints. The statistical approach toward secondary endpoints will be primarily descriptive; within-subject changes from baseline for each dosing group among-group differences will be evaluated.

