2.6 Descriptive Summaries

All tabulated summaries will include the two treatment groups and overall (includes data from both treatment groups). For endpoints that are continuous in nature: number of observations, mean, standard error of the mean (SEM),

median, minimum and maximum, and standard deviation (SD) values will be presented as descriptive summary. For endpoints that are categorical in nature: frequency counts and percentages will be presented in the descriptive summary.

The number of decimal places to display for calculated data will be determined by the original scale of the data. Means, medians, and confidence intervals will be reported with one (1) additional decimal place. Standard deviation will be reported with two (2) additional decimal places. Minimum and maximum will be reported with the same number of significant digits as the method of capture.

For all efficacy and safety tables summarizing change from baseline, the baseline and post-baseline results at all planned timepoints will be included.

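### The SAP calls for a between-group comparison of change in the efficacy scores but defines no between-arm difference or interval, and uses neither baseline score nor the stratification factor sex as a covariate

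*SAP*

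**What the plan says.** Three places call for a comparison between arms.

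- SAP section 5 names, as of particular interest, "a comparison between groups to evaluate any trends in differences between subjects randomized to active and placebo agents". Protocol section 10.4.3 says the same.
- SAP section 2.2 says that "within-subject changes from baseline for each dosing group among-group differences will be evaluated".
- Protocol section 10.4.1 says how: "all secondary endpoints will be summarized serially over time using descriptive statistics to assess the within-subject changes and between-group differences".

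The specification then stops at summaries by arm. SAP section 2.6 states "All tabulated summaries will include the two treatment groups and overall (includes data from both treatment groups"; the listed statistics are n, mean, SEM, median, minimum, maximum and SD, or counts and percentages. It adds that in change-from-baseline tables "the baseline and post-baseline results at all planned timepoints will be included". SAP sections 5.1 to 5.5 say only that changes, or ADCS-CGIC ratings, are summarised by timepoint. The titles of Tables 14.2.1 to 14.2.5 name no difference, interval or model. Confidence intervals appear once, in a formatting rule: "Means, medians, and confidence intervals will be reported with one (1) additional decimal place".

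On sex, SAP section 1.4 says "A stratified block randomization will be implemented by sex". After that it appears only among the demographic parameters in section 4.3.1.

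**The concern.** The comparison is named, but no quantity is attached to it. Two consequences follow.

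First, readers will see mean changes from roughly 11 and 5 subjects side by side, with no statement of how uncertain their difference is. Protocol section 2.2 expects these results to inform larger trials, so over-reading has a cost.

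Second, baseline is subtracted and displayed, so an imbalance would be visible, but it is not adjusted for. Subtracting baseline does not remove the effect of a chance imbalance. When the correlation between baseline and follow-up is below 1, the arm that starts higher tends to show a lower change. Over all randomisations this averages out; in the one trial that is run it does not. A reader can derive the unadjusted difference from the tabulated means and SEMs, but not a baseline-adjusted one.

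**Working it through.** **Inputs from the documents.** About 20 randomised 2:1 and about 16 evaluable (SAP 1.3); 20% drop-out (Protocol Summary). The drop-out figure reproduces: 16/(1 - 0.20) = 20.

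**Assumptions.** The visible text gives no SD, correlation, sex effect or confidence level. I use a two-sided 95% interval, equal variances at baseline and follow-up, and correlations (rho) of 0.5 to 0.9. Splits are 11:5 (about 16 subjects) and 13:7 (all 20). The Evaluable Dataset requires only four of the five doses, so its size may be nearer 20.

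**Unadjusted interval, in SDs of change.** Half-width = t × sqrt(1/n1 + 1/n2).

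- 11:5: sqrt(1/11 + 1/5) = 0.539; × t(14) = 2.145 gives 1.157.
- 13:7: sqrt(1/13 + 1/7) = 0.469; × t(18) = 2.101 gives 0.985.

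**Chance imbalance at baseline.** The difference in baseline means has the same SE, in baseline SDs.

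- 11:5: P(|imbalance| > 0.5 SD) = 2 × (1 - Phi(0.5/0.539)) = 0.354. The mean imbalance, given that active starts more than 0.5 SD higher, is 0.791 SD.
- 13:7: the corresponding figures are 0.286 and 0.740 SD.

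**Shift in the change-score difference.** Given such an imbalance, shift = -(1 - rho) × mean imbalance. The half-width in baseline SDs is the figure above × sqrt(2(1 - rho)).

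| rho | Shift, 11:5 | Half-width | Ratio | Shift, 13:7 | Half-width | Ratio |
|---|---|---|---|---|---|---|
| 0.5 | -0.396 | 1.157 | 34% | -0.370 | 0.985 | 38% |
| 0.7 | -0.237 | 0.896 | 26% | -0.222 | 0.763 | 29% |
| 0.8 | -0.158 | 0.732 | 22% | -0.148 | 0.623 | 24% |
| 0.9 | -0.079 | 0.517 | 15% | -0.074 | 0.440 | 17% |

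**What ANCOVA does to the shift.** Under a linear model the conditional shift is zero. In simulation with no treatment effect (8,000 runs per cell), ANCOVA with baseline and sex left it within 0.03 SD, with 94.5% to 95.5% coverage. A floor was also tried: integer MMSE-like scores with latent mean 3 or 5 and SD 4, clipped to 0-10 at baseline and 0-30 afterwards, so that 13% or 27% of subjects sit at 0. At 11:5 the change-score shift was then -0.38 to -0.02 SD, and ANCOVA stayed within 0.025 SD. That residual depends on the assumed floor.

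**Effect on interval width (simulated, against the change score, no sex effect).**

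| rho | Baseline + sex, 11:5, sex balanced | Same, random sex mix | Baseline + sex, 13:7, sex balanced | Same, random sex mix | Baseline only, 11:5 |
|---|---|---|---|---|---|
| 0.5 | -8% | -5% | -10% | -7% | -9.5% |
| 0.7 | -2% | +1% | -4% | -1% | -4% |
| 0.8 | +0.5% | +4% | -1% | +1.5% | -1% |
| 0.9 | +3.5% | +7% | +2% | +4% | +2% |

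The textbook ratio of residual SDs, with two degrees of freedom deducted, suggests 12% to 1% narrowing at 11:5. It is somewhat optimistic because it omits the cost of chance imbalance in the covariates. If sex does matter, the picture improves: with an assumed sex effect of 0.5 SD of change, balanced, 11:5, the width changes are -11%, -5%, -2.5% and 0% across the four correlations.

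**The case against.** The strongest reply is that the plan delivers what it promises. Both documents call the efficacy approach primarily descriptive, both arms are tabulated together with baseline shown, and an unadjusted difference can be worked out. The mock shells are a separate document not seen here, SAP section 10 allows tables to be modified, and part of the sample-size text is blacked out. This sets the weight of the point: no test, error rate or stated figure is affected. It does not supply an estimator, and a difference with an interval and no p-value is still descriptive.

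Second, the unadjusted interval keeps its nominal coverage over randomisations, and the shifts above condition on a notable imbalance in one direction, which has probability 0.354/2 = 18% at 11:5. Averaged over all allocations, the mean absolute imbalance is 0.539 × sqrt(2/pi) = 0.430 SD. The absolute shift is then 0.22, 0.13, 0.09 and 0.04 SD, or 19%, 14%, 12% and 8% of the half-width. Those figures are correct and describe the same effect over every allocation. An equal imbalance the other way gives a shift of the same size with opposite sign, so the larger figures apply in about one allocation in three.

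Third, sex costs a little width unless it predicts change, and with about five placebo subjects the cells are small. This stands. If the sponsor judges the term too costly, a baseline-adjusted difference with its interval is still worth having.

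Fourth, EVAL and PPROT depend partly on events after randomisation. No covariate adjustment repairs that selection, and unbiasedness over randomisations holds only to the extent that few subjects are lost.

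**Conclusion.** The point holds as an optional improvement. The SAP names a between-group comparison of change without defining a difference or an interval, and uses neither baseline nor sex as a covariate. At 11:5 to 13:7 the unadjusted interval is about ±1.16 to ±0.98 SD of change, and a baseline imbalance above 0.5 SD occurs in 35% to 29% of allocations. When it does, 15% to 38% of the half-width is a shift that data already collected can remove. The benefit is removal of that shift and a visible statement of uncertainty, not precision. The sizes rest on assumed splits, correlations and floor rates. Efficacy is secondary and unpowered, and the primary safety analysis is unaffected.

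**What to change.** In SAP section 5, for MMSE, SIB total, ADCS-ADL-Severe and NPI/NPI-NH, at each visit already tabulated, add the active-minus-placebo difference in change from an ANCOVA with treatment, baseline score and sex. Give a 95% CI, label it descriptive, report no p-value, and keep the existing summaries beside it. Tabulate the NPI version used by arm, without a version covariate. ADCS-CGIC has no baseline score: show the rating distribution by arm, with any between-arm contrast optional.

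The cost is a few SAP lines and one column in four tables. That makes 10 contrasts per analysis set (MMSE 2, SIB total 3, ADCS-ADL-Severe 1, NPI 2 visits × 2 scores = 4), or 20 over EVAL and PPROT. Three downsides should be accepted openly:

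- Two degrees of freedom are lost (t from 2.145 to 2.179 at 11:5; from 2.101 to 2.120 at 13:7).
- The interval is a few percent wider if the correlation is high or sex is unbalanced across arms. In an extreme mix (3 of 11 against 4 of 5), which stratification makes unlikely, it is 5% to 18% wider.
- Twenty intervals without multiplicity adjustment could be over-read. If the ten in one set were independent and no effect existed, the chance that at least one excludes zero would be 1 - 0.95^10 = 40%, and less with correlation. Hence the descriptive label.

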2 GENERAL ANALYSIS DEFINITIONS

All analysis dataset preparations and statistical analyses will be performed using SAS® version 9.4 or higher. No imputation will be performed for missing data unless stated otherwise. Listings for CSR Appendix 16.2 will include all the subject data points being collected or derived for analyses, and will be sorted by treatment group, site, and subject number.

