2.4 Analysis Datasets

- Screened Dataset (SCRN): All subjects who were screened and entered into EDC.
- Screen Failure Dataset (SCRF): All subjects who were entered as screen failures in the EDC.
- Intention-to-Treat Dataset (ITT): All randomized subjects.

- Safety Dataset (SAF): All subjects who received at least one dose of the study agent.
- Evaluable Dataset (EVAL): All subjects who receive at least 4 of the 5 planned doses.
- Per Protocol Dataset (PPROT): A subset of the Evaluable Dataset comprised of subjects who do not have any of the deviations listed below or any other deviation affecting efficacy identified prior to database lock.

Deviation Type	Deviation	Additional Clarification
Eligibility Inclusion Criteria Not Met	Diagnosis of AD based upon the National Institute on Aging-Alzheimer's Association (NIA-AA) Criteria	
Eligibility Inclusion Criteria Not Met	MMSE Score 0-10 inclusive	
Eligibility Inclusion Criteria Not Met	Modified Hachinski Ischemia Scale (MHIS) score of <=4	
Eligibility Inclusion Criteria Not Met	If on medications for cognition (e.g., rivastigmine, galantamine, donepezil, memantine), must be on stable dosage for at least 8 weeks prior to Baseline	Will be dependent upon timing of dose change
Eligibility Inclusion Criteria Not Met	If on daily antidepressant medications and/or benzodiazepines and/or typical or atypical antipsychotics, must be on stable dosage for 8 weeks prior to Baseline. If on prn dosing with atypical antipsychotics and/or benzodiazepines, these should not be given within 24 hours before each day of cognitive and other ratings (V1, V2, V8, V9, V10)	Will be dependent upon timing of dose change
Eligibility Exclusion Criteria Met	Evidence of clinically relevant neurological disorder(s) other than AD	
Eligibility Exclusion Criteria Met	Treatment with any human blood product, including transfusions and IV immunoglobulin, during the 6 months prior to screening	

Deviation Type	Deviation	Additional Clarification
Eligibility Exclusion Criteria Met	Concurrent participation in any other therapeutic treatment trial. If there was prior clinical trial participation, subject must have discontinued investigational agents for at least 30 days for small molecules, and 1 year for active or passive immunotherapies prior to Screening	
Eligibility Exclusion Criteria Met	Subjects who have a level of agitation that, in the opinion of the investigator, could interfere with study procedures	

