Eligibility Exclusion Criteria Met	Any other condition and/or situation that the investigator believes may interfere with the safety of the subject, the intent and conduct of the study, or interpretation of study data	Only when interfering with the interpretation of study data
Compliance	Incorrect treatment dispensed and administered to subject	
Out of Window	Efficacy Procedures performed outside of the protocol window which are a consistent pattern or potential risk to study data outcomes	
Study Drug Temp Excursion	Study drug temperature excursions when determined to have impacted the quality of the study drug	
Concomitant meds	Use of prohibited concomitant medications as defined in the protocol that have an effect on cognition	

Decisions regarding which subjects are included in the PPROT will be made before database lock.

A summary table of number (%) of subjects in each analysis set and applicable treatment assignment will be provided (Table 14.1.1).

The presentation of baseline characteristics will be conducted on the ITT dataset. All safety analyses will be performed for the SAF dataset. Analyses of the secondary endpoints will focus on the EVAL and/or PPROT datasets.

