5.2 Severe Impairment Battery (SIB)

The SIB is designed to assess cognitive abilities in patients with severe AD. The SIB is divided into scorable subscales that cover orientation to time and place, attention, language, praxis, visuospatial ability, construction, memory, orientation to name, and social interaction. Scoring gives credit to nonverbal and partially correct answers, thus decreasing the need for language output. There are 51 items, and it takes approximately 20 minutes to complete. The range of possible scores is 0-100 (Panisset 1994).

Although available in the raw data, the SIB scores will be recalculated. Changes from baseline for recalculated SIB subscale scores and the recalculated total score will be summarized at each scheduled timepoint (Days 6, 12, and 33) (Table 14.2.2).

5.3 Alzheimer's Disease Cooperative Study Group Activities of Daily Living Inventory for Severe Alzheimer's Disease (ADCS-ADL Severe)

The ADCS-ADL-Severe assesses the competence of patients with AD in performing basic activities of daily living. The ADCS-ADL-Severe contains 19 items covering physical and mental functioning and independence in self-care (e.g. dressing, grooming, bathing, eating, walking, and toileting). For each ADL, the informant (e.g., caregiver) is first asked if the patient attempted the activity during the past 4 weeks. If a patient did attempt the ADL, the informant is asked to choose the single most accurate definition of the patient's level of performance. The score ranges from 0 to 54, with higher scores indicating less functional impairment (Galasko 2005).

Although available in the raw data, the ADCS-ADL Severe total score will be recalculated. Changes from baseline for recalculated ADCS-ADL Severe total score will be summarized at the scheduled timepoint (Day 33) (Table 14.2.3).

5.4 Alzheimer's Disease Cooperative Study – Clinical Global Impression of Change Caregiver Input rating (ADCS-CGIC)

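### Efficacy is tabulated only for subjects with at least 4 doses, and early-termination results only if more than 5 such visits occur; an ITT version and a fixed rule would be a cheap improvement

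*SAP*

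**What the plan says.** **Analysis sets.** SAP 5 states: "Following efficacy endpoints will be analyzed based on both EVAL and PPROT sets". SAP 10 labels Tables 14.2.1 to 14.2.5 EVAL, PPROT and nothing else. SAP 2.4 defines EVAL as "All subjects who receive at least 4 of the 5 planned doses", and PPROT is a subset of it. ITT (everyone randomised) is also defined there, but for efficacy it is used only in Listings 16.2.6.1 to 16.2.6.5 (SAP 11).

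**Early-termination (ET) results.** SAP 5 says that "results at early termination visits will not be included in tabulated summaries unless the number of early termination visits is > 5". SAP 2 adds: "No imputation will be performed for missing data unless stated otherwise".

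**Aim.** Among the things of particular interest, SAP 5 lists "a comparison between groups to evaluate any trends in differences between subjects randomized to active and placebo agents". The same section says that the study is not powered for efficacy, and SAP 2.2 calls the approach to secondary endpoints primarily descriptive.

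**Protocol.** Section 10.3 says that analyses of secondary endpoints will focus on the Evaluable and/or Per Protocol Datasets, and 10.4.1 says that final analyses are not limited to the summaries it describes. Section 7.3.7 asks sites to attempt the full End of Study battery when a subject with at least one infusion leaves early. The schedule in 15.1 gives End of Study and ET one shared column.

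**The concern.** The number of doses received and early exit are both determined after randomisation, and either may differ between the arms. A table restricted by them compares selected parts of the two arms.

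The ET rule adds three problems.

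- **The count has no stated basis.** It depends on the data, and the number of ET visits says nothing about whether a given assessment is valid.
- **It cannot be programmed without further decisions.** The unit is not given (the study total is the most natural reading), nor is the destination of the results once the count is passed: Day 33 or a row of their own. Those choices could be made late, with the data in view.
- **It interacts with the EVAL restriction.** Even when the count is passed, ET results from subjects with fewer than 4 doses stay out, because those subjects are not in EVAL.

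A subject who leaves after dose 4 or 5 keeps a baseline and any scheduled visits attended, since SAP 2.6 says that "the baseline and post-baseline results at all planned timepoints will be included". That subject has no tabulated end-of-study change unless the count is passed. For ADCS-ADL-Severe there is then no tabulated change at all, because Day 33 is its only post-baseline timepoint (SAP 5.3).

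At stake is how representative the descriptive efficacy tables are. Protocol 2.2 expects the study's results to inform larger trials.

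**Working it through.** **Inputs**

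- N = about 20, randomised 2:1 (SAP 1.3). Arms: 20 × 2/3 = 13.3 and 20 × 1/3 = 6.7, so about 13 and 7.
- Dropout 20% (Protocol Summary, Population). The range 10% to 30% is my assumption.
- Trigger: more than 5 ET visits, that is 6 or more (SAP 5), read as a study total.
- Assumption: each dropout independently gives one ET visit.

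**The plan's own figure.** 20 × (1 − 0.20) = 16, which reproduces the stated approximately 16 evaluable subjects.

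**Chance that the rule bites.** Let X be the number of ET visits, X ~ Binomial(N, p). Expected number at plan: 20 × 0.20 = 4, below the trigger.

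- P(tabulated) = P(X ≥ 6)
- P(ET results exist, none tabulated) = P(1 ≤ X ≤ 5) = 1 − P(X = 0) − P(X ≥ 6)

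At N = 20 and p = 0.20: P(X = 0) = 0.80^20 = 0.0115 and P(X ≥ 6) = 0.1958, so P(1 ≤ X ≤ 5) = 1 − 0.0115 − 0.1958 = 0.793.

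| Scenario | N | p | P(X ≥ 6) | P(1 ≤ X ≤ 5) |
|---|---|---|---|---|
| 10% dropout | 20 | 0.10 | 0.011 | 0.867 |
| Planned dropout | 20 | 0.20 | 0.196 | 0.793 |
| 30% dropout | 20 | 0.30 | 0.584 | 0.416 |
| 20% dropout, 75% of dropouts attend ET (0.20 × 0.75) | 20 | 0.15 | 0.067 | 0.894 |
| 20% dropout, replacement raises N to 25 | 25 | 0.20 | 0.383 | 0.613 |

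The last two rows rest on assumed attendance and replacement figures.

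**The unit matters.** If the count were per arm at 20% dropout, P(X ≥ 6) would be 0.030 with 13 subjects and 0.0004 with 7. The placebo arm would almost never reach it.

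**Subjects with fewer than 4 doses.** The documents give no number. Protocol 5.4.2 aims for about 16 subjects with 5 doses who complete Visit 8, so 20 − 16 = 4 fall short at planned dropout. Between 0 and 4 of these could have had fewer than 4 doses. One such subject is 1/13 = 8% of the active arm or 1/7 = 14% of the placebo arm.

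**What this does not measure.** The 20% describes the yield of evaluable subjects; it is not a rate of ET visits. Someone who leaves after Visit 8 adds an ET visit without counting against that yield. Someone never dosed, or whose consent is withdrawn, may have no ET visit. X also includes ET visits from subjects whom EVAL excludes whatever the count. So 0.79 is the chance that the trigger goes unmet while ET results exist. It says nothing about the direction or size of bias, and no readable figure in the documents would give either.

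**The case against.** A reader might infer that the SAP contradicts itself by seeking a comparison of subjects as randomised and then not tabulating it. The documents do not support that. The phrase in SAP 5 can simply name the two arms; protocol 10.4.3 uses the same phrase, and protocol 10.3 directs secondary endpoints to the Evaluable and Per Protocol sets. Nothing commits efficacy to ITT, so the SAP does not depart from the protocol.

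The other side has more to say:

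- **No inference is at stake.** The primary endpoint is safety, analysed on all dosed subjects. This stands, and it limits the severity.
- **The values are disclosed.** The ITT listings carry the efficacy values and are sorted by treatment group. Table 14.1.1 gives the size of each analysis set, and Tables 14.1.2, 14.1.8.2 and 14.1.10 give disposition, infusions completed and visit attendance. With about 20 subjects that is substantial disclosure. It stands, although a listing is not a summary by group.
- **A minimum count may have a purpose.** Four ET results split 2:1 would give means on about 3 and 1 values, at irregular times. ADCS-ADL-Severe asks about the past 4 weeks, so a rating soon after dosing may largely describe the period before treatment. These are good reasons not to fold every ET result into Day 33. They do not explain why a sixth visit should change the treatment of the other five, and the SAP offers no such reason.
- **Keeping all ET results apart from Day 33 would be too rigid.** A last visit at Day 5 plus the roughly 4 weeks allowed by protocol 5.4.2 falls at about Day 33. This is right, and the fix allows for it.

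**Conclusion.** The point holds as a cheap improvement worth making. As written, the efficacy tables omit subjects with fewer than 4 doses, and they probably omit ET results too. At the planned dropout, ET results exist but go untabulated with probability about 0.79, and from 0.42 to 0.87 over assumed dropout of 30% down to 10%. This rests on 20 subjects, independent dropout, one ET visit per dropout and a study-wide count.

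The tabulated comparison is therefore selected on post-randomisation events, by a rule whose basis, unit and destination are unstated. The harm is modest. It would be wrong to read 0.79 as a measure of bias, or to conclude that the efficacy comparison is invalid.

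**What to change.** 1. In SAP 5 and SAP 10, add an ITT version of Tables 14.2.1 to 14.2.5: randomised subjects with available data, by assigned arm. Keep the EVAL and PPROT versions.
2. Replace the sentence with the > 5 count by: *Early-termination results are always tabulated by treatment group. An assessment within Day 33 ± 7 days is summarised at Day 33; any other is shown in a separate Early termination row with its study day.*

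Protocol 10.3 and 10.4.1 leave room for this, so a note in SAP 8 is optional.

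**Cost.** SAP wording, one more population and one extra row in five tables; no new data and no change to visits.

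**Limits.** The extra row will hold few values at irregular times, including ADCS-ADL-Severe ratings whose 4-week recall may reach back before treatment. Randomised subjects who were never dosed may add nothing, since the ET visit is asked only of subjects with at least one infusion. Without imputation, the scheduled rows still show only those who attended. The gain is the ET results themselves, plus any scheduled results from subjects who stopped dosing early but stayed in follow-up. It does not restore a complete Day 33 comparison of the randomised groups.
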